Overview. At baseline, we will obtain self-report measures (see below), height and weight, a blood sample for A1C, and accelerometer data for physical activity. At each intervention phone session, interventionists will collect feasibility and acceptability data (see below). At the follow-up visit (8 weeks), a blinded assessor will obtain repeat self-report data, vitals, A1C, and accelerometer data. At 16 weeks, a blinded assessor will obtain self-report data by telephone, and an accelerometer will be mailed to the participant to measure physical activity. All participants will receive pedometers, free parking or public transportation at all visits, \$20

after the second visit, \$40 after the 8-week follow-up visit, and \$40 after the 16-week phone assessment, after all devices have been returned.-

Initial/Enrollment Visit (in-person visit #1). We will collect data on basic sociodemographic variables (age, gender, race/ethnicity, living alone, duration of T2D, medical/psychiatric comorbidities, medications) needed to characterize our population (and to be used as part of randomization by minimization). Next, participants will complete self-report measures, and we will draw blood for A1C if participants did not have these procedures completed as part of a clinical visit (if they had A1C in the last 3 weeks, including this visit, we will use that value to prevent subjecting participants to the blood draw). This visit will occur on site, partially in offices in the Warren building and partially in the MGH Corrigan Minehan Heart Center. Finally, participants will be given an accelerometer, which will be worn over the subsequent week (prior to visit #2) to measure baseline physical activity.

Objective physical activity assessment and in-person visit #2. In order to gather baseline physical activity data, participants will take home and wear accelerometers for 1 week prior to visit #2. During in-person visit #2, participants will return their accelerometers and will begin the study intervention, as outlined below.

Intervention (PP-MI vs. MI alone: 8 weekly phone sessions).

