5A’s model (all sessions)	Interventionists: (a) Ask about progress on the prior cognitive (e.g., pros/cons of becoming active) or physical activity goal, (b) Advise about the benefits of physical activity on health and function, (c) Assess current stage of change and barriers/facilitators to change, (d) Assist with setting a goal, and (e) Arrange the next phone session.
Session-specific topics	Session 1: Introduction to MI tools and tracking of physical activity Session 2: Setting a SMART (Specific, Measurable, Attainable, Relevant, Time-based) activity goal Session 3: Identifying barriers and problem-solving around them Session 4: Using social and equipment resources Session 5: Finding new walking routes (neighborhood walkability audit) Session 6: Using neighborhood resources Session 7: Managing slips Session 8: Reducing sedentary time/taking breaks Session 9: Planning for the future

Walkability audit. Built environment audits (see attachment) can promote physical activity by helping participants find new opportunities for physical activity, manage environmental barriers, and change perceptions about their environment.^{76,77} PP-MI participants will complete the 15-item Microscale Audit of Pedestrian Streetscapes-Mini (MAPS-Mini),⁷⁸ a walkability audit that has participants identify walkways, parks, traffic, and other features in their neighborhood and usual walking routes by completing checklists as they explore these areas. Participants will be oriented to MAPS-Mini administration in session 5 and complete it in the

next week. Information from this audit will be used during MI sessions to facilitate the setting of practical physical activity goals based in participants' local areas.

Training and fidelity. All team interventionists have delivered PP-MI. Once the intervention is refined for T2D, they will receive additional training via didactics, role play, and supervised interviews. During the study, weekly interventionist supervision will be led by PI [name] (PP content) and [name] (MI). All sessions will be recorded; supervising study staff (Drs. [name], [name], [name], or [name]) will rate a random selection (20% at minimum) for fidelity using scales for the PP and MI components, respectively, and provide feedback.

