To measure physical activity, we will use the ActiGraph GT3X+ accelerometer,⁸² a small, silent device without readout that is worn at the hip and stores data for several weeks; it has been validated and used in many populations, including T2D, to measure habitual physical activity.⁸³ The GT3X+ is a half-dollar-sized device that is very lightweight, clips to a belt or

shoe, and has no sharp edges, shock risk, or visible readout (or any identifying data). Participants will wear the devices for 7 days. We will consider 5 valid days of wear (8+ hours per day) to be sufficient; participants will re-wear devices if needed. In a recently completed PP-MI study in ACS patients (n=128; PHS IRB# 2014P001756), we used these devices/methods with good results. Sedentary time will also be measured with Actigraphs, using protocols to differentiate between sedentary time and device non-wear.^{84,85} Data will be downloaded onto our study team's local computers without need to transmit data to external servers.

D. Procedures

A single venous blood sample will be collected at baseline and 8 weeks by study staff trained in phlebotomy, for A1C. No other procedures will be performed.

E. Data collected and when the data is to be collected (see Table 1, below)

Baseline characteristics. To allow us to better understand our study population (and to allow for limited/qualitative accounting for covariates, we will record subjects' baseline characteristics (age, gender, race/ethnicity, duration of diabetes diagnosis, medical and psychiatric comorbidities, medications, and baseline lipids, and hemoglobin A1c). Data will be obtained at the initial interview and supplemented with information from medical records.

Feasibility and acceptability (*Aim 1; # of PP-MI sessions completed, participant ratings of PP-MI ease and utility*). Interventionists will record completion of PP-MI sessions at each session (weeks 1-8). A completed PP-MI session requires both: (i) PP exercise completion and phone discussion, and (ii) the MI portion of the call must end with a specific physical activity-based goal for the next week. In addition, at intervention calls, participants will separately report ease and utility (0-10 scales) of the prior week's PP exercise and MI-based goal-setting, for 4 total ratings per session.

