- For self-reported physical activity, we will use the IPAQ, well-validated in diverse settings.
- For self-reported smoking history, we will use the Cigarette Use Questionnaire.
- For self-reported alcohol use, we will use the Alcohol Use Disorder Identification Test – Consumption (AUDIT-C).

Medical outcomes (*Aim #3; exploratory*). At baseline and follow-up, we will also measure weight and A1C.

Table 1. Schedule of study events/assessments.

	Pre-enrollment	Enrollment	Weeks 1-8	Week 8	Week 16
Assessment for inclusion criteria (T2D, IPAQ)	X				
Assessment for exclusion criteria (e.g., cognitive screen, other medical conditions limiting activity)	X				
Interview and chart review for baseline characteristics		X			
Self-report measures		X		X	X
Vital signs (weight) and A1C*		X		X	
Accelerometer (MVPA and sedentary time)		X		X	X
PP-MI exercise sessions			X		
Session ratings by participants (ease/utility)			X		

*Will use values from clinical visit (or within 3 weeks in the case of A1C) if available.

VI. Biostatistical analyses:

A and B. Specific data variables and study endpoints

Specific Aim 1 (*feasibility and acceptability*): To determine whether the PP-MI intervention is feasible (assessed by % of total PP-MI phone sessions completed) and well-accepted (assessed by participant ratings of the ease and utility of each PP-MI session) among T2D patients with low baseline activity.

Measures:

- Rates of completion of exercises (recorded by study trainer)

Specific Aim 2 (physical activity): To assess whether PP-MI is associated with larger increases in MVPA, and less sedentary time, on accelerometer at 8 and 16 weeks, compared to MI.

Measures:

- MVPA in mean minutes per day
- Sedentary time in mean minutes per day

Specific Aim 3 (additional outcomes): To explore whether the PP-MI intervention is associated with greater improvements on other psychological, behavioral, and medical outcomes, compared to MI.

Measures:

- Psychological measures: PANAS, LOT-R, SEE, HADS, BRS, MSPSS
- Behavioral measures: SDSCA, % medication adherence, IPAQ, PF-20, PDI
- Medical outcomes: Weight, BMI, and A1C

C. Statistical methods

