Confidentiality. To minimize confidentiality-related risks, we will use participant ID numbers—as opposed to identifiable personal data or medical record numbers—on all study documents. We will discuss only information that is related directly to the study with subjects' clinicians, and we will use locked cabinets and offices as well as password-protected databases to store personal information. Information from self-report assessments will be collected and stored using the secure, HIPPA-compliant, firewalled, and password-protected REDCap system. REDCap is a free web-based application developed for management of research and clinical data; it has separate password-protected data collection repositories for each trial. We have used this system for numerous prior studies without difficulty. Accelerometers will be labeled only with participant numbers; they will be connected to staff computers via USB and staff will utilize the password-protected Actigraph software downloaded onto our local computers to obtain activity data. No personally identifiable information will be recorded physically or electronically onto the accelerometers or within the software program.

Finally, digital recordings of PP-MI and MI sessions will be completed using portable recorders. Randomly-selected sessions will be reviewed for competence and adherence to the protocol by supervising study staff members (e.g., Project Director, PI) using PP and MI fidelity rating scales. For sessions in the MI alone condition, supervising study staff will complete fidelity ratings with additional rating items to ensure that interventionists are not delivering PP content or other content (e.g., related to sedentary time) specific to PP-MI. All recordings will be downloaded immediately from the recorders and the electronic files will be kept within the firewalled, password-protected shared file area for fidelity review. Recordings will contain no personally identifiable information (and study interventionists will be specifically trained not to use names or other identifying information on the recordings) and will be erased following review. We have used all of these methods to maintain confidentiality in prior projects using the same measures, data repository, accelerometers, and recorders.

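### The treating interventionist collects the ease/utility ratings and records session completion, with no stated independent check, so both primary Aim 1 endpoints are at risk of upward bias of unknown size

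*Combined protocol and SAP*

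**What the plan says.** **Who collects.** V.A (Overview): "At each intervention phone session, interventionists will collect feasibility and acceptability data". V.E (Feasibility and acceptability): "Interventionists will record completion of PP-MI sessions at each session (weeks 1-8". In the same paragraph, at the intervention calls, "participants will separately report ease and utility (0-10 scales", with four ratings per session covering the PP exercise and the MI goal-setting. The Aim 1 measures in section VI (A and B) use another label for the recorder: "Rates of completion of exercises (recorded by study trainer". The documents do not say whether the trainer and the interventionist are different people.

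**What counts as complete.** V.E requires two things: "PP exercise completion and phone discussion", and "the MI portion of the call must end with a specific physical activity-based goal for the next week".

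**What is reviewed.** All sessions are recorded. Under Training and fidelity in V.A, supervising staff "will rate a random selection (20% at minimum) for fidelity using scales for the PP and MI components". Section VII.D (Confidentiality) describes the purpose: "Randomly-selected sessions will be reviewed for competence and adherence to the protocol by supervising study staff members". It adds that recordings are erased once reviewed. The monitoring section has the PI and biostatistician check REDCap entry and transfer to Stata.

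**What rests on it.** Section II makes these the primary hypotheses: a majority of the 30 PP-MI participants complete at least 6 of 8 sessions, and mean ratings exceed 7/10.

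**The concern.** Participants rate each week's exercise and goal-setting by phone, in a call with the person who delivers the intervention. That setting invites courtesy ratings. The same person records whether the session met the completion rule, and the second criterion (that the call ended with a specific activity goal) depends partly on how that person ran the call. The MI component in V.A also allows cognitive work as well as activity steps, so some calls will be borderline.

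The supervisors' review is not described as confirming completion status, and the REDCap review concerns data entry. Both bars are absolute and apply to PP-MI alone, so a shift in the ratings or the completion record would not cancel against a comparator as it might in a between-arm contrast. Ratings may also be examined after 10 and/or 20 participants if barriers to acceptability are suspected (Outcomes monitoring), and inflated ratings could hide a problem that could still be corrected.

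**Working it through.** **Inputs from VI.D:** n=30; expected mean 7.8, SD 1.8, bar 7.0; within-person correlation 0.5; completion 75% against 50%, two-sided alpha 0.05. **From V.E:** 4 ratings per session over 8 weeks, so 4 × 8 = 32 per participant if none is missed. **Assumed, not in the documents:** the true mean, the size of any inflation and the rate of miscounting.

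**1. The plan's own figures.**
- *Feasibility.* By the exact binomial, at least 21 of 30 has probability 0.021 at 50% and 0.803 at 75%, which matches the stated 80%.
- *Ratings.* SE = 1.8 × √[(1 + (m − 1) × 0.5)/m] / √30 for m ratings per person. With m=32, SE = √[1.8² × (0.5 + 0.5/32)/30] = 0.236. Two-sided power is Φ(0.8/0.236 − 1.96) = 0.924. With m=4, SE = 0.260 and one-sided power is 0.924. Either is close to the stated 93%; two-sided with m=4 gives 0.869.

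The issue does not alter these power figures. It concerns whether what is recorded equals what is true.

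**2. Ratings under assumed inflation.** Take a true mean of 6.7 (just short of the bar), m=32 and SE 0.236. Section II and the descriptive analysis in VI.C allow any observed mean above 7 to count as success. The power statement in VI.D implies a test, for which the observed mean must exceed 7 + 1.96 × 0.236 = 7.46. Both rules are shown.

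| Assumed inflation | Expected observed mean | P(observed mean > 7) | P(observed mean > 7.46) |
|---|---|---|---|
| 0 | 6.7 | 1 − Φ(0.3/0.236) ≈ 10% | about 0.1% |
| 0.3 | 7.0 | 50% | 2.5% |
| 0.5 | 7.2 | Φ(0.2/0.236) ≈ 80% | 1 − Φ(0.26/0.236) ≈ 13% |

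The assumption of 32 ratings matters little. With 24 per person, SE = √[1.8² × (0.5 + 0.5/24)/30] = 0.237.

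**3. Completion under assumed miscounting.** Suppose exactly 50% of participants truly meet the rule and a fraction f of true non-completers is recorded as completers. The recorded rate is then 0.5 + 0.5f.

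| f | Recorded rate | P(at least 21 of 30) | P(at least 16 of 30, a bare majority) |
|---|---|---|---|
| 0 | 0.50 | 2.1% | 43% |
| 10% | 0.55 | 6.9% | 64% |
| 20% | 0.60 | 17.6% | 82% |

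**4. Reach of the existing review.** If all planned calls take place, PP-MI has 30 × 8 = 240 sessions, and 20% of these is 48. The recordings needed to check completion on that sample are already being listened to.

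**The case against.** A reader might infer that the interventionist alone decides what counts as complete. The documents do not support that. They say the interventionist records completion against a written two-part rule, every call is recorded, supervision is weekly, and at least 20% of sessions are rated. Reviewing the exercise and setting a goal are scripted parts of each call, so an adherence review may well cover the same ground. The content of the fidelity scales is not given. What can be said is that no check of completion is stated, not that none would occur.

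A reader might also infer that the primary endpoints do lean toward success. Nothing in the documents shows that bias is present or how large it is, so only a risk can be claimed.

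The contrast with the blinded 8- and 16-week assessors is limited. Blinding to condition protects comparisons between arms, and Aim 1 concerns one arm only. The relevant safeguard is separating the person who delivers treatment from the person who collects the rating.

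Nor do the documents make the ratings a formal progression rule. Section II mentions further testing in the sentence on MVPA and other key outcomes. Dropout, and participant reports at follow-up, give other signals of acceptability.

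Finally, collecting ratings during the call limits missing data and recall error, so changing it is a trade-off. All of these points stand. They narrow the concern but do not supply the missing check.

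**Conclusion.** The concern holds as a risk. The treating interventionist collects the ratings and records completion for the two primary endpoints, and no independent verification of either is described. The direction of plausible bias is upward, and its size is unknown.

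The consequence depends heavily on the success rule. With a true mean of 6.7 and an assumed 0.5 points of inflation, the chance of success is about 80% if any observed mean above 7 suffices, but about 13% if 7.0 must be significantly exceeded. For completion, miscounting an assumed 20% of non-completers raises the chance of reaching 21 of 30 from 2.1% to 17.6% when the true rate is 50%. These figures rest on the plan's SD, correlation and sample size, and on assumed true values and bias sizes. They are illustrations, not estimates. Sample size and stated power are unaffected.

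**What to change.** **1. Completion (V.A Training and fidelity; VII.D Confidentiality).** Add the two criteria from V.E to the form supervisors already use on the 20% or more of reviewed recordings. Score them before erasure and without sight of the interventionist's entry. Correct discordant sessions and report agreement. *Cost:* two items on an existing form for about 48 PP-MI sessions, fewer if calls are missed. Supervising staff include the PI, so this is a second look rather than a fully independent one.

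**2. Ratings (V.E).** Have participants enter the four ratings themselves after each call through a REDCap link. Eligibility requires only a phone, so those without internet should be able to mail back a manual page or read the ratings to a coordinator. Tell participants that the interventionist does not see individual ratings. Do not rely on a page returned only at week 8: it would lose the ratings of people who drop out, who may be the less satisfied, and could itself push the mean upward. *Cost:* one form or manual page and some coordinator time for prompts. Some ratings will be missed, so report the number received per session and the results with and without participants who drop out.

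**3. Wording.** State in section VI who the study trainer is in relation to the interventionist.

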Session 7: Using personal strengths, part 2 ²⁴	Participants identify a second signature strength, then find a specific new way to use that strength in the next 7 days.
Session 8: Acts of kindness ⁶²	Participants complete three acts of kindness, planned or spontaneous, in a single day.
Session 9: Planning for the future	Participants review the positive psychology skills they learned in the program, then make a plan to use their skills in the future.

MI component of PP-MI. This will be adapted from our PP-MI program in ACS patients, [name] MI interventions,¹⁰⁻¹² and data from T2D patients. The MI portion of calls (15 mins) will assess participant motivation to increase physical activity (safe, specific activity goals will be obtained from their medical providers), and plan action steps or cognitive work to boost motivation. We will use established models of goal-setting and feedback based in social cognitive theory^{67,68} and the transtheoretical model of behavior change⁶⁹ that utilize setting of proximal, attainable, explicit goals and specific feedback to reinforce progress and enhance self-efficacy. We will typically focus on walking, as brisk walking is feasible as a first step in becoming active for T2D patients⁷⁰ and can improve health.⁷¹ The ultimate physical activity goal in nearly all cases will be moderate physical activity for ≥ 150 min/week, per ADA guidelines.⁴³ Gradual, safe physical activity progression will be ensured via a stepwise approach, symptom monitoring, and coordination with participants’ physicians. Participants will also be given a digital pedometer (Omron) that clips on a belt or other article of clothing, to promote and track physical activity. Finally, this enhanced MI program will also focus on reduction of sedentary time by helping participants to track sitting time and develop strategies to reduce such episodes,⁷²⁻⁷⁴ using the framework for increasing physical activity and our team’s experience with sedentary time interventions.⁷⁵ Participants will be mailed a graph of their weekly step counts two times over the course of the study. The graph updates will be sent at the middle and end of the study (i.e. following sessions 4 and 8).

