MI-based health behavior education condition (time matched). The MI-based health behavior education intervention was selected as the control condition for several reasons. The inclusion of MI and education regarding key diabetes health behaviors aims to increase the retention of participants included in this condition. However, the focus of this intervention on multiple health behaviors and the lack of specific physical activity goal-setting make it less likely that this control intervention will significantly impact physical activity (our primary health behavior outcome). Finally, as an attentional control, it has a parallel structure to the experimental arm with a treatment manual, weekly exercises, and weekly calls to review exercises.

Each week, participants will learn about a different health behavior topic related to diabetes health. They will also be introduced to motivational interviewing topics in concert with the health behavior education topics. The intervention is divided into four sections, focusing on different important diabetes health-related topics:

Part One: Diabetes Self-care

How to Take Care of Your Diabetes (*Session 1*)

Participants will review information about the importance of self-care (e.g., glucose monitoring, foot checks, eye exams) to reduce the risk of T2D complications.

Part Two: Medication Adherence

Taking Medications Regularly (*Session 2*)

Participants will review the importance of medication adherence and learn about medications typically prescribed for T2D. Participants will be encouraged to create a list of their current medications, as well as any questions they have for their physicians about their medications.

Barriers to and Resources for Taking Medications Regularly (*Session 3*)

Participants will identify barriers to taking medications, problem-solve those barriers, and identify resources to help them maintain adherence to medications.

Part Three: Staying Active

The Importance of Staying Active (*Session 4*)

Participants will review the cardiovascular benefits of physical activity, questions to ask their physician prior to starting physical activity, and ways to set goals related to physical activity.

How You Can Stay Active (*Session 5*)

Participants will identify one way in which they wish to change their physical activity. They will discuss the importance of making the change and their confidence about being able to do so. Finally, they will create a list of pros and cons for behavior change.

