Hypoglycemia. Some medications for T2D (i.e., insulin, sulfonylureas, repaglinide, nateglinide) can lead to hypoglycemia, and patients increasing their activity may become hypoglycemic. To address this for all participants who are on medications that can lower glucose, we will provide specific verbal and written guidance about symptoms of hypoglycemia, self-monitoring of blood glucose, and management of hypoglycemia, using handouts and protocols adapted from the NIDDK-funded Look AHEAD and REAL HEALTH-Diabetes (Look AHEAD implementation) studies focused on increasing activity in patients with T2D.^{103,104} Participants in both groups will also be given contact information for the study team and will be asked to contact the study team if hypoglycemia occurs during exercise. At all calls and follow-up assessments, interventionists and study staff will also query participants who are currently taking medications known to predispose patients to hypoglycemia during exercise (i.e., insulin, meglitinides, or sulfonylureas) about signs and symptoms of hypoglycemia. If such symptoms arise, the study endocrinologist ([name]) will coordinate with participants' medical care providers (and evaluate participants by phone or in-person as needed) to assist in making medication and other care adjustments to address these episodes, utilizing the approach used by [name] when managing T2D participants on glucose-lowering medications in REAL HEALTH-Diabetes. Patients who are not currently taking medications known to increase risk of hypoglycemia during physical activity will not be asked about hypoglycemia symptoms at every call, in order to minimize participant burden. However, these participants will still be encouraged to notify their interventionist should they experience any symptoms of hypoglycemia.

Physical activity safety. To ensure that patients can safely participate in physical activity, we will confirm with the patient's clinician (physician or nurse practitioner) that the patient is

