Serious Adverse Events. Expedited review will occur for all events meeting the definition of Serious Adverse Events (SAEs); i.e., any fatal event, immediately life-threatening event, permanently or substantially disabling event, or event requiring or prolonging inpatient hospitalization. This also includes any event that a study investigator or the DSMB judges to impose a significant hazard, contraindication, side effect, or precaution. All relevant information will be reported to the DSMB for each SAE including information about the event and its outcome, study group assignment, medications, the subject's medical history and current conditions, and any relevant laboratory data. Notification by e-mail and FAX transmittal of all related study forms shall be made to the DSMB. Information will be reviewed and a determination made of possible relevance to the study.

Non-Serious Adverse Events. At periodic intervals determined by the DSMB (e.g., quarterly during the study and then again at its completion), the DSMB will be provided with unblinded summaries of the numbers and rates of adverse events by treatment group. These reports will include types of events, severity, and treatment phase. Data on individual non-serious adverse events is not expected to be needed for this review.

Other Safety-Related Reports. At quarterly intervals, the DSMB will also receive unblinded summary reports of treatment retention and reasons for drop-out, by treatment arm and study phase.

Study Stopping Rules. If at any time during the course of the study, the DSMB judges that risk to participants outweighs the potential benefits, the DSMB shall have the discretion and responsibility to recommend that the study be terminated.

Monitoring of Data Quality by the DSMB. At least on a quarterly basis during the course of the study, the DSMB will receive a report on data quality and completeness. [name] (study biostatistician) will prepare these reports in collaboration with [name]. At a minimum, this will include an overview of the progress of patient intake and retention; summary reports describing patient compliance with evaluations as described in the protocol; and a summary of the completeness and quality of key data elements needed to characterize patients,

study interventions, and primary and secondary outcomes. These reports will be used by the DSMB to evaluate the capacity of the data capture and processing to support scientifically valid analyses.

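### Adverse events are compared by arm without a common scheduled question, while activity review at every session is described only for PP-MI

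*Combined protocol and SAP*

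**What the plan says.** **PP-MI calls.** Section V.A (MI component of PP-MI) states: "Gradual, safe physical activity progression will be ensured via a stepwise approach, symptom monitoring, and coordination with" the participants' physicians. It gives no frequency, script or symptom list. The 5A's table, marked as applying to all sessions, has the interventionist ask "about progress on the prior cognitive (e.g., pros/cons of becoming active) or physical activity goal" and assess barriers and facilitators. Under V.E, a PP-MI session counts as complete only if it ends with a specific activity goal.

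**Control calls.** Section V.A (MI-based health behavior education condition) says of the control that "it has a parallel structure to the experimental arm with a treatment manual, weekly exercises, and weekly calls to review exercises". Its content differs: "Each week, participants will learn about a different health behavior topic related to diabetes health". Activity is the topic in sessions 4, 5 and 6; the others cover self-care, medication, diet and future planning. The section notes that "the lack of specific physical activity goal-setting make it less likely that this control intervention will significantly impact physical activity". No activity-linked symptom monitoring is described.

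**Both arms.** Section VII.D (Hypoglycemia) says: "At all calls and follow-up assessments, interventionists and study staff will also query participants who are currently taking medications" that raise the risk of hypoglycemia. Selection is by drug, not by arm. Under Physical activity safety in VII.D, clinicians are asked for cautions and warning signs for participants in either condition, and interventionists escalate concerning symptoms. VII.D closes with a general request that subjects report adverse events related to participation. The Patient Alert System covers admissions and emergency visits at Partners hospitals.

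**Use of the data.** Under Safety monitoring, the DSMB receives "unblinded summaries of the numbers and rates of adverse events by treatment group", and individual data on non-serious events are not expected to be needed.

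**The concern.** A by-arm comparison of event rates is fair only if events are looked for equally in both arms. Here the conversation that would most naturally bring out an activity-related complaint takes place at every PP-MI session and in three control sessions. Nothing scheduled and common to both arms makes up the difference for events that are neither hypoglycemic nor serious enough to reach a hospital.

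An apparent excess in PP-MI could then be more frequent asking, a real effect of greater activity, or both. Conversely, a problem among control participants, who also receive pedometers and three activity sessions, could go unrecorded. Route of detection cannot be reconstructed reliably once the calls are over.

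**Working it through.** **1. Is there a plan figure to reproduce?** No. The documents give no adverse event rate, detection probability, safety margin or safety power. Section VI lists no adverse event analysis.

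**2. Ascertainment routes side by side**

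| Route | PP-MI | Control |
|---|---|---|
| Weekly calls | Yes | Yes |
| Hypoglycemia query at all calls and follow-ups (by drug) | Yes | Yes |
| Clinician warning signs; concerning-symptoms pathway | Yes | Yes |
| General adverse event request | Yes, unscheduled | Yes, unscheduled |
| Partners hospital alerts | Yes | Yes |
| Review of goals and barriers at every session | Yes | Not described |
| Activity-linked symptom monitoring | Yes, frequency not stated | Not described |
| Activity as session topic | All sessions | Sessions 4-6 |

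The last three rows differ. Of the shared routes, the concerning-symptoms pathway says what to do once a symptom is known, not how to find it. The general request has no timing or wording. Table 1 has no adverse event row, and the V.A overview lists only feasibility and acceptability data for collection at intervention calls. The common routes therefore do not assure equal ascertainment of non-serious, non-hypoglycemic events.

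**3. Illustration of size (all detection values and event rates are assumptions)**

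Let q be the true probability that a participant has such an event, equal in both arms, and let d be the probability that it is recorded.

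- Expected count per arm = 30 × q × d
- Apparent ratio = (q × d_PP-MI) / (q × d_control) = d_PP-MI / d_control

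At q = 0.20 with 30 per arm:

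| d, PP-MI | d, control | Expected counts | Ratio |
|---|---|---|---|
| 0.90 | 0.75 | 30×0.20×0.90 = 5.4; 30×0.20×0.75 = 4.5 | 1.20 |
| 0.90 | 0.60 | 5.4; 3.6 | 1.50 |
| 1 | 3/8 | 6.0; 2.25 | 2.67 |

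The last row is an extreme: events surface only in activity-focused calls, eight against three, with no later recall. Even that fraction is not firm, because both arms list nine session topics against eight weekly calls.

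Over q from 0.10 to 0.40, the chance of a nominal two-sided p < 0.05 in these rows would be about 4-7%, 6-17% and 16-59%. The DSMB applies no such test; this only gives scale.

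**4. With equal asking.** If d is the same in both arms it cancels and the ratio is 1.0, for example 5.4 against 5.4 at d = 0.90. For hypoglycemia the documented query is already the same in both arms.

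**The case against.** The strongest reply is that most safety procedures are arm-neutral. A reader might infer that symptoms are monitored in PP-MI only; the Hypoglycemia and Physical activity safety text in VII.D contradicts that. A reader might also infer weekly symptom monitoring, or active elicitation of falls and joint complaints in PP-MI. The documents state neither. The phrase in V.A has no frequency and may merely summarise the safety procedures in VII.D. The 5A's question concerns progress on a goal, not symptoms. These points stand.

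The direction of bias can also be questioned. Control sessions on self-care and medication might bring out other kinds of event. That is fair, and it is why the point is limited to activity-related events.

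Nor is the by-arm summary the only view of harm. The DSMB reviews every serious event and receives retention and dropout reasons by arm. Blinded staff collect pain disability, physical function and HADS scores in both arms at baseline, 8 and 16 weeks. There is no event-rate boundary; stopping is at the DSMB's discretion. This limits the consequence but does not remove it, because that discretion draws on these summaries and they would not show how an event was found.

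Finally, a PP-MI excess could be real, since the intervention aims to raise activity. That is the difficulty: the summary could not separate the two explanations.

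**Conclusion.** The point holds in a limited form. Review of activity goals and barriers at every session, and activity-linked symptom monitoring, are described only for PP-MI. The general adverse event request has no schedule or common wording, and rates go to the DSMB by arm. Non-serious, non-hypoglycemic activity-related events may therefore be found more often in PP-MI. Hypoglycemia and Partners hospital events are much less exposed.

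Neither the size nor the certainty of the bias can be derived from the documents. The ratios of 1.20, 1.50 and 2.67 rest wholly on assumed detection values. A reader might take them as a forecast that PP-MI will look less safe by some such factor; nothing in the documents supports that.

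This is a cheap improvement to data collection. It does not call the primary feasibility and acceptability aim into question.

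**What to change.** - Add one identically worded adverse event question to every intervention call in both arms and to the week-8 and week-16 assessments, and add the matching row to Table 1. Ask it at the start of the call, before any intervention content, so that PP-MI activity review does not pre-empt it. Keep the wording free of intervention content so that it does not unblind the follow-up assessor.
- Record answers on one REDCap form with a field for route of detection: common question, volunteered, hypoglycemia query, intervention review or hospital alert.
- Report all events to the DSMB by arm and by route. Use common-question events as the like-for-like comparison, and exclude no events. Restricting the rates to that question alone would drop volunteered and alert-detected events.
- Leave the existing safety procedures in both arms as they are.
- Reconcile two passages: V.A says the control lacks specific activity goal-setting, while VII.D describes to clinicians a plan for setting activity goals in either condition.

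Cost: about a minute per call, so about 8 minutes per participant over eight calls and 60 × 8 = 480 minutes (8 hours) if all 60 participants complete them, plus the two assessments and one form. The recorded event count will rise. The question equalises asking; it cannot fully equalise how closely participants attend to their own symptoms.
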